7.6 Duration of Therapy and Follow-Up

All study participants will be followed through their 2nd home visit, approximately 1-year after their 1st home visit unless they withdraw consent from the study prior. All participants following the 2nd home visit will receive a copy of their clinically relevant results embedded in a SCP. As mentioned above, those on the control arm can then have the option of having a 30 minute counseling session to review those results and the SCP with the study clinician.

8.0 STUDY PROCEDURES

An overview of study procedures can be found in **Table 3**.

TABLE 3. Summary of required observations.

	Initial home visit	Baseline counseling session	4-month booster	2 nd home visit
Intervention group	Questionnaires* Anthropometrics Blood draw	Goals/Action Plan Call duration Call fidelity	Rating of Action Plan completion	Questionnaires* Anthropometrics Blood draw
Control group	Same as intervention group	-	-	Same as intervention group
Primary healthcare provider(s)	-	-	-	Provider survey Clinical records
Time window to complete	<2 mo of enrollment (max: <6 mo)	<2mo of home visit (max: <3 mo)	3-5 mo from baseline	11-15 mo from 1 st home visit (no max))

*Participants will be asked to complete the questionnaires prior to the scheduling of their home visits.

8.1 Baseline Questionnaire

This will include items on: 1) past medical history, 2) current health and medication adherence, 3) lifestyle habits, and 4) attitudes towards healthcare and current mood (**Table 4; Appendix**).

TABLE 4. Components of baseline questionnaire, exclusive of questions on past medical history and lifestyle habits.

*Health-related self-efficacy⁵⁶	10-item (4-point Likert scale) survey (will be reduced to 5-items) that measures perceived ability to set-goals, cope and recover from setbacks. Results have been found to be a strong predictor of subsequent health behavior change. ⁹⁶
*PROMIS anxiety & depression^{57,58}	These domains (adult 4-item survey; all 5-point Likert scale) are of secondary interest. Prior research via a longer instrument (Profile of Mood States) did not show SCPs associated with mood changes or anxiety. ^{50,85}
*Multidimensional Health Locus of Control [MHLC]⁵⁹	18-item survey (6-point Likert scale) will classify participants with regards to their attitudes towards healthcare screening into “worried”, “collaborative” and “self-controlling” typologies, which have been associated with differential likelihoods of obtaining recommended screening in retrospective CCSS analyses. ⁷⁸
*Medication Adherence Scale (MMAS-4)⁶⁰	Well-established 4-item (0=high, 1-2=medium, 3-4=low adherence) instrument initially used to study hypertension, but since validated for other diseases. ¹⁰⁰ Will be administered separately for blood pressure, lipid, and diabetes medications. Secondary analyses will examine adherence by medication burden.

8.2 First Home Visit

This will include:

- Signature on HIPAA authorization and Medical Record Release form (optional).
- Standing height: in centimeters, to the nearest 0.1 cm.
- Weight: in kilograms, to the nearest 0.1 kg.
- Blood pressure at rest: 3 times; each at least 3 minutes apart.
- Waist circumference: in centimeters, to the nearest 0.1 cm; just above the uppermost lateral border of the right ilium [hip bone]; at the end of a normal expiration.
- Blood draw (no fasting required): lipid profile, blood glucose, hemoglobin A1c, insulin, and samples for ancillary biological studies (**Table 5**).

TABLE 5. Overview of blood samples, draw order, vial type, volume.

Draw order / Analyte	Vial type	Volume
1) Lipid profile, glucose, insulin level*	Heparin plasma separator tube (green top)	3.0 mL
2) Hemoglobin A1c*	EDTA tube (lavender top)	1.0 mL
3) Protein & DNA-based assays	EDTA tube (lavender top)	7.5 mL
4) General chemistries	Serum separator tube (red/gray top)	7.5 mL
5) Proteomics, metabolomics	EDTA separator tube (pearl)	7.5 mL
6) RNA for gene expression	PAXgene tube	2.5 mL

*These also will be drawn at the 2nd home visit; remaining tubes would NOT be drawn at the 2nd home visit unless they could not be successfully drawn at the first visit. 2nd home visit only: blood spot offered for failed venous draws.

With our 7/2020 protocol modification, in response to the unexpected closure of the study's original exam service provider (EMSI), replacement service providers may include those that do not provide home-based services but rather fixed laboratory / service centers that the participant travels to in order to obtain the specified research blood draw. In these instances, only tubes 1-2 (**Table 5**) will be drawn and processed on-site (i.e., tubes 3-6 will not be drawn).

Rarely, in past experiences with our pilot data and similar CCSS home visit-based studies, exam service staff will be unsuccessful in obtaining blood given technical issues. In this situation, the participant will be offered the choice of having the procedure be rescheduled to another date. *If the participant refuses and the primary study endpoints (lipid profile, blood glucose, and hemoglobin A1c) cannot be collected, then the patient will not be eligible to continue on the study.* Any partial results will still be sent back to the participant and their designated primary care provider.

8.3 Baseline Counseling Session (Intervention Group)

A printed SCP with personalized health history, recommendations, and clinically meaningful results from the home visit (i.e., average blood pressure, lipid profile, diabetes screening, BMI) will first be sent to survivors on the intervention arm. Interpretation of these results is as defined in **Section 3.3.1**. We will then schedule participants for a remote counseling session by phone or web video, per participant choice). This will be scheduled as soon as possible following the initial home visit with a goal of having this being completed within 2 months of the home visit. Sessions completed outside of the 2-month window will be flagged (but remain eligible for analysis). The following outcomes will be measured at this time point:

- Creation of a personalized goals and action plan (**Appendix**).

- Counseling session completion rates, with goal of obtaining $\geq 85\%$ completion within 2 months of the initial home visit.
- Call duration, with goal of achieving $\geq 85\%$ being ≤ 30 minutes in duration.
- Study clinician fidelity to the intervention. Fidelity will be scored using standard methods across 8 levels with the 8th a global rating (**Appendix**). Trainers will review audiotapes of sessions, with fidelity ratings and feedback to the clinician until the mean of 4 consecutive global ratings are ≥ 3.5 (scale: 0 [poor] to 5 [very good]). Once certified, trainers will review audio recordings and complete fidelity ratings for 15% of sessions, more if fidelity dips below a global rating of 3 (satisfactory) for 3 of 10 sessions.

It is possible that some randomized participants will fail to schedule a session despite multiple contact attempts. *We will cease scheduling attempts if no session has been scheduled by 3 months after the initial home visit.* These participants will not be eligible for the 4 month booster session (discussed below). However, we will still attempt to re-assess their health status at the 1-year time point with a 2nd questionnaire and home visit. *If a participant has to cancel and reschedule, the rescheduled date can fall outside the 3 month deadline and we will attempt to do the booster session within the target time range still.*

8.4 Baseline Return of Results (Control Group)

Survivors in the control arm will receive a copy of clinically meaningful baseline home visit results, with a general recommendation to seek medical follow-up in instances where any of those values are abnormal since we consider it unethical to withhold such information. Interpretation of these results is as defined in **Section 3.3.1**. A copy also will be sent to their designated healthcare provider. These will be issued within one month of the home visit.

8.5 Handling of Critical Results

Staff will be asked to ship out blood samples within 24 hours (could be slightly longer on weekends) of collection, and data forms will be faxed, both to the CCSS data coordination center at St. Jude. Once received, labs will be processed in real-time (i.e., not batched) by the CLIA-certified lab at St. Jude.

Copies of data forms and any examiner shipping manifest will be forwarded to the study team at FHCRC. In the event that a critical test result is found (see **Table 6**), the PI or his designee, will attempt to notify the participant more quickly by phone to seek medical follow-up (rather than waiting for a letter to be generated and mailed to the participant). This process is similar to and adapted from that used by the CDC-sponsored NHANES for their in-person mobile assessments.

TABLE 6. Classification of test results, as discussed in Section 8.5.

	Goal	Borderline	Abnormal	Critical
Systolic blood pressure (mmHg)*	<120	120-129 systolic	130-179	≥ 180
Diastolic blood pressure (mmHg)	<80		80-119	≥ 120
LDL cholesterol (mg/dL)	<130	130-159	≥ 160	-
Triglyceride (mg/dL), if fasted ≥ 10 hrs	<150	-	150-749	≥ 750
Triglyceride (mg/dL), if not fasting	<200	-	200-749	≥ 750
Glucose (mg/dL), if fasted ≥ 8 hrs	<100	100-125	126-299	$\geq 300^{\dagger}$ or $\leq 50^{\ddagger}$
Glucose (mg/dL), if not fasting	<140	140-199	200-299	$\geq 300^{\dagger}$ or $\leq 50^{\ddagger}$
Hemoglobin A1c (%)	<5.7	5.7-6.4	≥ 6.5	-

*We will drop the highest of 3 systolic measurements, and average the remaining 2 for systolic & diastolic values. [†]If not previously known to have a diagnosis of diabetes. [‡]If known diabetic only, as this would be concerning for therapy-related hypoglycemia.

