3.3 Study Design

The study's first primary aim will be answered by recruiting a cross-sectional sample of predicted high CV risk patients. Those who meet eligibility criteria will then be randomized to a controlled intervention with delayed intervention controls to answer the study's second and third primary aims.

3.3.1 Primary Aim 1 Endpoint: Prevalence of underdiagnosis and undertreatment of the following target CV conditions. *Underdiagnosis* defined for each as:

- Hypertension: Joint National Committee (JNC7/8)^{47,48} considers systolic 120-139 and diastolic pressures 80-89 mmHg to be suggestive of pre-hypertension; *lifestyle intervention* is recommended.^{47,49} Hypertension is suspected if systolic ≥ 140 or diastolic ≥ 90 mmHg, and in addition to lifestyle modification, *pharmacologic treatment* is recommended for adults <60 years (treatment threshold ≥ 150 systolic if ≥ 60 years).⁴⁸ We will ascertain the prevalence of pre-hypertension and hypertension; both may be eligible for Aim 2. *However, with the introduction of the 2017 ACC/AHA hypertension guidelines, the classification system has shifted such that systolic ≥ 130 or diastolic ≥ 80 mmHg are now considered Stage 1+ hypertension (with treatment threshold reduced accordingly).*⁵⁰ As such, *with our 12/2017 protocol modification, we will adopt these slightly more stringent thresholds for eligibility and drop the prior “pre-hypertension” category.*
- Dyslipidemia: American Heart Association and American Academy of Pediatrics recommend intervening (*lifestyle modification first; if unsuccessful, consider pharmacologic therapy*) among childhood cancer survivors for LDL ≥ 160 mg/dL or fasting triglyceride ≥ 150 mg/dL.⁵¹ As fasting blood draws are not as commonly done in most primary care settings now for initial screening, for non-fasting (<10 hours) samples, a triglyceride ≥ 200 mg/dL is considered high. This study will use these cut-points to define dyslipidemia. These thresholds were largely in-line with

those defined by a recent NIH-sponsored expert panel,⁵² and largely similar to prior NCEP Adult Treatment Panel recommendations.⁵³

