5.0 SUBJECT ELIGIBILITY

5.1 Inclusion Criteria

For Primary Aim 1:

- 5.1.1 CCSS participant who is age ≥ 18 years at time of initial consent.
- 5.1.2 High CV risk status based on CCSS risk prediction models for cardiomyopathy and ischemic heart disease.
- 5.1.3 Living in the U.S., within 50 miles of a designated exam service provider (e.g., EMSI) based on CCSS's available contact information at the time of approach.
- 5.1.4 Able to read, write, and speak English.
- 5.1.5 Ability to understand and the willingness to provide informed consent.

For Primary Aim 2, in addition to the satisfying the above criteria, participants must also meet the following criteria:

5.1.6 Abnormal CV condition identified on home visit. Defined as having at least one of the following:

- Average blood pressure $\geq 130/80$ mmHg ($\geq 130/80$ if existing hypertension diagnosis)
- LDL ≥ 160 mg/dL
- Triglyceride ≥ 150 mg/dL (if ≥ 10 hours fast) or ≥ 200 mg/dL (if < 10 hours fast)
- If not known to be diabetic: Glucose ≥ 100 mg/dL (if ≥ 8 hours fast) or ≥ 140 mg/dL (if < 8 hours fast)
- HbA1c $\geq 5.7\%$ (if not known to be diabetic), HbA1c $\geq 7\%$ (if known diabetic).

5.1.7 Be free of any known (self-reported) ischemic heart disease or cardiomyopathy.

5.1.8 Have access to a telephone or computer to receive a phone or web video counseling/intervention session at baseline and at 4 months.

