13.0 STATISTICAL CONSIDERATIONS

13.1 Aim 1 Analytic Plan

Hypothesis: Approximately 60% of participants will have an abnormal CV risk-factor finding that meets clinical intervention thresholds, and among those with abnormalities, 40% will be undertreated and 80% newly diagnosed.

Primary analyses: We will calculate the prevalence of hypertension, dyslipidemia, and diabetes by self-report and by physiologic measurement. We will then calculate the proportions (with exact 95% confidence intervals) of participants who may be underdiagnosed as well as the proportions undertreated (like **Figure 3**). We will calculate the prevalence of directly measured pre-diabetes separately. **Secondary analyses:** We will examine whether rates differ by: sex; current age; time since cancer diagnosis; obese ($BMI \geq 30 \text{ kg/m}^2$) vs. not; health insurance vs. not; recent history of being seen in a dedicated long-term follow-up clinic for survivors vs. not; and lifestyle factors (smoking, low fruit/vegetable intake, low physical activity).

Sample size considerations: Based on prevalence estimates from CCSS surveys and our pilot (**Table 2, Figure 3**), we expect ~60% of high CV risk participants ($n \sim 480$) to have an abnormal CV risk factor measurement; prevalence of individual risk factors ranging 20-40% (less when stratified by underdiagnosis/undertreatment status). With an overall sample $n=800$, we expect reasonable precision for our primary prevalence estimates (**Table 9**). Power to detect differences <10% in secondary analyses may be more limited.

TABLE 9. Estimated power for Aim 1 analyses.		
Prevalence \pm 95% CI	Minimum detectable proportions*	
N=800	N=320:480	N=200:200
5% \pm 1.5%	5% vs. 1/11%	5% vs. 0/14%
20% \pm 2.8%	20% vs. 12/29%	20% vs. 10/33%
50% \pm 3.5%	50% vs. 40/60%	50% vs. 36/64%

*2-sample Fisher's exact test, 80% power, $\alpha=0.05$.

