Secondary analyses: In case survivors who were newly diagnosed (i.e., underdiagnosed) following their 1st home visit differ in their response to the intervention vs. those previously diagnosed but undertreated, we will examine estimates stratified by diagnosis status at the 1st home visit. For similar reasons, we also will examine estimates if pre-diabetes are excluded. In our primary model, we also will explore whether differences vary by sex, current age, time since cancer diagnosis, obese (BMI ≥ 30 kg/m²) vs. not, health insurance vs. not, and recent history of being seen in a dedicated long-term follow-up clinic for survivors vs. not. We also will explore, among intervention participants, whether action plan scores from the 4-month session are associated with differential undertreatment rates (as a single parameter). Finally, we plan to also compare across the study arms, the measured CV risk factor values from the 2nd home visit separately: 1) average systolic pressure, 2) average diastolic pressure, 3) LDL, 4) triglyceride, 5) blood glucose, and 6) HbA1c. For this subanalysis we will use linear models, adjusting for the value at the 1st home visit as a covariate.

Sample size considerations: Assuming 60% of Aim 1 participants (n=800) meet Aim 2 eligibility with a subsequent conservative 20% drop-out rate, ~380 survivors (190/arm) would have complete data. The study would be 80% powered ($\alpha=0.05$) to detect RRs ≤ 0.88 (i.e., $\geq 12\%$ reduction in the intervention vs. control group) if the prevalence of having an undertreated CV risk factor among controls after the 2nd home visit was 90% (10% reduction from baseline). If controls had an unlikely 50% reduction, we can still detect RRs ≤ 0.71 . Analyses stratified by initial underdiagnosis or undertreatment status (~75-150/arm) will be able to detect RRs ≤ 0.79 to ≤ 0.86 , respectively. Systematic reviews have reported RRs 0.6-0.8 for strategies similar our proposed interventions in the general population.^{64,65} For continuous outcomes (secondary analyses), we will be powered to detect change equaling $\sim 30\%$ of 1 standard deviation, which equates to 5 mmHg systolic blood pressure, 3 mmHg diastolic pressure, 10 mg/dL LDL, 30 mg/dL triglyceride, 10 mg/dL glucose, and 0.3% HbA1c. Differences within these ranges have been reported by others for interventions conducted in the general population.⁶⁶⁻⁶⁸

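### The only blood-pressure averaging rule drops the highest systolic reading, which can only lower Aim 1 hypertension prevalence on the systolic criterion; Aim 1 should use an average fixed in advance and report both.

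*Combined protocol and SAP*

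**What the plan says.** Section 8.2 specifies the readings: "Blood pressure at rest: 3 times; each at least 3 minutes apart". Section 8.7 repeats the three readings at the second visit, in both arms.

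The one instruction for turning three readings into a single value is the footnote to Table 6 in Section 8.5: "We will drop the highest of 3 systolic measurements, and average the remaining 2 for systolic & diastolic values". Table 6 classifies results for return and for critical notification. Its abnormal range starts at 130 systolic and 80 diastolic, the same limits as the study cut-point.

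The sections that define the endpoints do not name an averaging rule:

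- Section 3.3.1 gives only the cut-point: systolic of at least 130 or diastolic of at least 80 mmHg "are now considered Stage 1+ hypertension".
- Section 5.1.6 says only "Average blood pressure".
- Section 13.1 describes the Aim 1 estimate: "We will then calculate the proportions (with exact 95% confidence intervals) of participants who may be underdiagnosed as well as the proportions undertreated". It then says of n=800 that "we expect reasonable precision for our primary prevalence estimates", with Table 9 giving 5% ± 1.5, 20% ± 2.8 and 50% ± 3.5 points.

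The documents give no reason for dropping the highest reading and plan no sensitivity analysis with another average.

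**The concern.** A rule that discards a reading because it is the highest chooses data by the quantity being measured. It always removes the systolic reading most likely to cross 130 mmHg. If settling-in is the worry, a rule based on order, such as leaving out the first reading, deals with it without looking at the values.

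The stake is Aim 1. Prevalence of underdiagnosed and undertreated hypertension is part of its primary endpoint and will be reported with exact confidence intervals. Those intervals describe sampling error. A shift caused by the averaging rule does not shrink as n grows and is not visible in them.

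**Working it through.** **Inputs from the documents.** Three readings per visit (8.2); the drop-highest rule (Table 6 footnote); cut-point 130 or 80 mmHg (3.3.1); N=800 and the half-widths of Table 9 (13.1); "prevalence of individual risk factors ranging 20-40" per cent (13.1). Section 13.2 equates about 30% of one SD with fixed differences, "which equates to 5 mmHg systolic blood pressure, 3 mmHg diastolic pressure", which implies SDs of 5/0.30 = 16.7 mmHg systolic and 3/0.30 = 10 mmHg diastolic.

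**Assumptions not in the documents.** Within-visit systolic SD (s) of 2-8 mmHg; within-visit diastolic SD of 0.7s; population mean from 116/71 to 128/79; between-person systolic-diastolic correlation 0.7; within-visit correlation 0 to 0.7; first-reading elevation 0 to 10 mmHg. Applying the Section 13.2 SDs to the Aim 1 cohort is also an assumption.

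**Step 1: the plan's own figure.** Half-width = 1.96 × sqrt(p(1-p)/800). This gives 1.51 points at 5%, 2.77 at 20% and 3.46 at 50%, so Table 9 reproduces (exact intervals: 1.58, 2.83, 3.52). The same formula gives 3.2 at 30% and 3.4 at 40%.

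**Step 2: direction.** For any participant, the mean of the two lowest systolic readings is no greater than the mean of all three, and no greater than the mean of any two chosen by position. This needs no distributional assumption.

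**Step 3: expected systolic shift.** For three exchangeable normal readings the expected maximum is 0.846s above the mean. The other two then average 0.846s/2 = 0.423s below it:

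| s (mmHg) | 2 | 3 | 4 | 5 | 6 | 8 |
|---|---|---|---|---|---|---|
| shift (mmHg) | -0.85 | -1.3 | -1.7 | -2.1 | -2.5 | -3.4 |

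**Step 4: systolic criterion alone.** Shifted prevalence = P(Z > z + 0.423s/16.7). At a true 20%, z = 0.842:

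- s = 3: P(Z > 0.918) = 17.9%, a fall of 2.1 points.
- s = 4: P(Z > 0.943) = 17.3%, a fall of 2.7 points.
- s = 8: P(Z > 1.044) = 14.8%, a fall of 5.2 points.

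The fall matches Table 9's 2.8 points at s of about 4.

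**Step 5: the study's criterion, 130 or 80.** This was simulated. The diastolic average uses the same two readings, so it also falls on average if the two pressures rise and fall together within a visit. Shift in prevalence against the three-reading mean, exchangeable readings, within-visit correlation 0.5, over the four population means:

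| s (mmHg) | shift (points) |
|---|---|
| 2 | -1.4 to -1.7 |
| 3 | -2.0 to -2.5 |
| 4 | -2.7 to -3.3 |
| 5 | -3.3 to -4.1 |
| 8 | -4.9 to -6.8 |

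Correlation matters. At s = 5 and mean 120/74 the shift is -2.1 points with no within-visit correlation, -3.8 at 0.5 and -4.4 at 0.7. Allowing for lower correlation widens the ranges to about 1 to 2.5 points at s of 2-3, 2 to 4 at 5, and 3 to 6 or more at 8.

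**Step 6: a raised first reading.** Taking the mean of readings 2 and 3 as the comparator (mean 120/74, correlation 0.5):

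| first reading high by | s = 3 | s = 5 |
|---|---|---|
| 0 mmHg | -2.4 | -4.1 |
| 4 mmHg | -0.5 | -1.7 |
| 6 mmHg | -0.1 | -1.0 |

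When the first reading is usually the highest, dropping the highest and dropping the first are nearly the same rule.

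**The case against.** Three objections carry weight.

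*Scope.* The footnote belongs to a table about classifying and notifying results, and Sections 3.3.1 and 13.1 do not cite it. That it governs Aim 1 is an inference, so calling the Aim 1 analysis wrong as written would go too far. The inference is nevertheless reasonable: no other rule exists, and the table's 130/80 limits match the Aim 1 cut-point. If the footnote does not apply, a primary endpoint has no stated derivation. Either way the analysis section needs a sentence.

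*Size.* A reader might infer that the bias is about as large as the stated precision, or larger. The documents do not support this. They give no within-visit SD. At 3 mmHg the fall at 20% is 2.1 points, below the stated 2.8, and at 2 mmHg the combined shift is about half the stated precision. Reaching it takes an SD of about 4 mmHg or more, exchangeable readings, and pressures that vary together within a visit.

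*Truth.* The three-reading mean is not true prevalence. Section 8.10 accepts that in-person readings can misclassify in either direction compared with home monitoring. What is shown is a difference between averaging rules, not the net error against usual blood pressure.

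A reader might also infer that the Aim 2 comparison is biased. It is not: both arms are measured and averaged the same way. The rule may lower the number eligible and the event rate, but it does not favour an arm.

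**Conclusion.** The point holds as a conditional one. Selecting readings by value can only lower or leave unchanged measured systolic pressure and the proportion at or above 130 mmHg, relative to all three readings or any fixed-order pair. That direction is certain for the systolic criterion. For the combined criterion it is the expected direction when within-visit systolic and diastolic readings vary together.

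The size is not known from the documents. Against the three-reading mean it may equal or exceed Table 9's 2.8 to 3.5 points from a within-visit SD of about 4 mmHg; below that it is smaller. Against readings 2 and 3, with a first reading 4-6 mmHg high, it is only about 0 to 2 points at an SD of 3-5. How the shift divides between the underdiagnosed and the undertreated was not computed. This is a cheap improvement to the Aim 1 estimate and does not threaten the trial.

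**What to change.** State in Sections 3.3.1 and 13.1 that Aim 1 prevalence uses an average fixed before the values are seen: either all three readings, or the second and third. Name one of these as primary, because they differ from each other if the first reading runs high. Report the drop-highest prevalence alongside as a sensitivity analysis.

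Leave trial eligibility, the results returned to participants and the Aim 2 endpoint rule as they are. No repeat of the Aim 2 analysis is needed on this account.

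The cost is a changed derivation from readings already taken, provided each one is recorded. The downside is that the reported research prevalence may differ slightly from the classification returned to participants and used for trial entry; a footnote to the results table can say so.
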